COVID-19 Vaccine Response in People Living with Sickle Cell Disease

PROTOCOL NO.:

ASH RC CTN 2021-00001
WCG IRB Protocol #20212379

PROTOCOL VERSION: 2.0
PROTOCOL DATE: 14Apr2022

SPONSOR: American Society of Hematology Research Collaborative

Study Principal Investigators:

[name]
University of Pennsylvania

[name]
Johns Hopkins University

Participating Sites: TBD

Table of Contents

Study Summary.....	3
1 Background and Study Rationale.....	4
2 Study Objectives	4
3 Investigational Plan	5
3.1 Study Endpoints	5
4 Study Population and Duration of Participation	5
4.1 Inclusion Criteria.....	5
4.2 Exclusion Criteria	5
4.3 Subject Recruitment	6
4.4 Vulnerable Populations:	6
5 Study Procedures	6
5.1 Informed Consent.....	6
5.2 Medical Record Review.....	7
5.3 Questionnaires	7
5.4 Blood Draw.....	8
5.5 Schedule of Events	8
5.5.1 Visit 1.....	8
5.5.2 Visit 2.....	9
5.5.3 Visit 3.....	9
5.5.4 Visit 4.....	9
5.5.5 Visit 5.....	9
5.5.6 Visit 6.....	10
5.5.7 Unscheduled Visits.....	10
5.6 Subject Withdrawal and Early Termination	10
6 Statistical Plan.....	11
7 Safety and Adverse Events	11
8 Study Administration, Data Handling and Record Keeping.....	12
8.1 Confidentiality	12
8.2 Data Collection and Management.....	12
9 Study Monitoring.....	12
10 Ethical Considerations	12
10.1 Risks.....	13
10.2 Benefits	13
10.3 Risk Benefit Assessment.....	13
11 Study Finances.....	13
11.1 Funding Source	13
11.2 Subject Payments	13
12 References.....	13
Appendix A: Schedule of Events.....	15

Study Summary

Title	COVID-19 Vaccine Response in People Living with Sickle Cell Disease
Short Title	COVID-19 Vaccine Response in Sickle Cell Disease
Study Population and Duration	Up to 200 subjects with sickle cell disease will be enrolled at up to 20 sites in the United States. Subjects will participate in the study for approximately 6 months.
Objectives	
Primary Objective: to measure antibody response to COVID-19 vaccination in a cohort of persons with SCD.
 
Secondary Objective: to assess for unexpected side effects of COVID-19 vaccination in a cohort of persons with SCD.

Main Inclusion and Exclusion Criteria	
Inclusion Criteria
 
 1. Diagnosis of sickle cell disease (HbSS, HbSC, HbSB⁰ thalassemia, HbSB⁺ thalassemia, HbS/Other) 2. Has not received any COVID vaccination prior to enrollment 3. Scheduled for a COVID vaccination (type does not matter) as part of routine care 4. Willing to sign consent 
Exclusion Criteria
 
 1. Unwilling to have labs drawn or complete study requirements. 2. Previous therapy curative of SCD (including bone marrow transplant and gene therapy) 3. Previous receipt of anti-COVID-19 antibody therapy

1 Background and Study Rationale

Sickle cell disease (SCD) is a genetic disorder caused by a single base substitution of valine for a glutamine at the sixth amino acid of the gene encoding for the hemoglobin β chain. Patients with Hgb SS disease or other sickle hemoglobinopathies suffer from a variety of clinical complications related to this abnormal hemoglobin.

These clinical manifestations include hemolytic anemia and painful or vaso-occlusive crisis that occurs when sludging in the microcirculation causes tissue hypoxia. In addition to the painful events, SCD patients generally auto-splenectomize in childhood secondary to infarctions from their hemoglobinopathy¹, thus increasing their risk of infection and rendering them immunosuppressed.

Patients with SCD are considered at increased risk of complications from infection from SARS-CoV-2 infection and are therefore an important group to receive vaccination against the virus. In data published from a COIVD-19 registry, 69% of patients with SCD diagnosed with COVID-19 were hospitalized, 11% required ICU admission and 7% died.² The mean patient age was <40 years, raising significant concern about the risks associated with COVID-19 infection in individuals with SCD.

Data suggest that general immune function in SCD patients may be impaired, and thus responses to vaccine may be suboptimal. One example is the decreased efficacy of hepatitis B vaccination in children with SCD. Although this vaccine is highly effective in the general pediatric population, a clinical trial in children with SCD showed that only 89% of subjects achieved a protective antibody level of ≥ 10 mIU/mL as compared to 97% of controls ($p=0.002$). However, 93% of the children who did not achieve protective immunity after the standard series of 3 doses of vaccine did achieve a protective titer after receiving a 4th dose, suggesting that a successful outcome can be achieved with a modified vaccination schedule³. There are multiple abnormalities in adaptive immunity in SCD which may explain decreased vaccine efficacy. A recent study demonstrated that sickle cell patients have an increased number of CD4+CD28null cells as compared to age- and race-matched controls, and in vitro studies have demonstrated these cells release high levels of pro-inflammatory cytokines. Treatment with hydroxyurea was demonstrated to decrease this dysfunctional immune cell population.⁴ In addition, SCD patients have been shown to have a skewing of T helper cells towards a Th2 phenotype and a reduction in the ratio of CD4 helper to CD8+ T suppressor cells, both of which may contribute to a mild state of immunosuppression in SCD patients.⁵

These differences in immune cell populations have been characterized in vitro, but there is little evidence in the literature as to how this may affect SCD patients' ability to respond to vaccine antigens as well as infectious diseases. Concerns have been raised about response to vaccination to influenza⁶, and the effect of the use of hydroxyurea on the seroconversion post yellow fever vaccination in people with SCD.⁷ Understanding response to COVID-19 vaccination in this high-risk group of patients can provide a more targeted approach to vaccination and an assessment of whether additional doses of vaccine will be required in order to achieve adequate protection.

2 Study Objectives

- **Primary Objective:** to measure antibody response to COVID-19 vaccination in a cohort of persons with SCD.

- **Secondary Objective:** to assess for unexpected side effects of COVID-19 vaccination in a cohort of persons with SCD.

3 Investigational Plan

The purpose of this project is to monitor the antibody response to vaccination in this immunosuppressed population and assess for unexpected side effects from vaccination. Subjects with sickle cell disease who are eligible to receive their initial COVID-19 vaccination will be recruited and asked to provide informed consent. Prior to receiving COVID-19 vaccination, subjects will visit the study site to complete questionnaires and provide a blood sample. Following vaccination, subjects will be contacted by phone, text, or email to complete a survey (2 to 3 total). Subjects will return to the study site 2 and 6 months after vaccination to complete questionnaires and provide a blood sample. Blood samples will be analyzed for antibody response to the COVID-19 vaccine.

3.1 Study Endpoints

- **Primary endpoint:** IgG ELISA titer geometric mean at 2 months (56 days) after the initial vaccination.
- **Secondary endpoints:**
 - IgG ELISA titer geometric mean at 6 months after initial vaccination.
 - Side effects of vaccination and sickle cell related consequences of those side effects, as assessed by patient report and through validated survey instruments including ASCQ-Me, the Brief COPE scale and the Brief Pain Inventory for participants 18+ years of age, and PROMIS Pain Interference, and PROMIS Mobility for pediatric participants.
 - Incidence of patient reported COVID-19 infections in the 6-months following immunization with the COVID-19 vaccine.

4 Study Population and Duration of Participation

Up to 200 subjects will be enrolled at up to 20 sites in the United States. Subjects will participate in the study for approximately 6 months.

4.1 Inclusion Criteria

1. Diagnosis of sickle cell disease (HbSS, HbSC, HbSB⁰ thalassemia, HbSB⁺ thalassemia, HbS/Other)
2. Has not received any COVID-19 vaccination prior to enrollment
3. Scheduled for a COVID-19 vaccination (type does not matter) as part of routine clinical care*
4. Willing and able to sign consent

4.2 Exclusion Criteria

1. Unwilling to have labs drawn or complete study requirements.
2. Previous therapy curative of SCD (including bone marrow transplant and gene therapy)
3. Previous receipt of anti-COVID-19 antibody therapy

** Note: Inclusion Criteria #3 should be interpreted as the subject having made the decision to get vaccinated and having identified when and where they will be vaccinated. A subject's confirmation of their intent to get vaccinated, and the approximate date of their vaccination is sufficient to meet this inclusion criteria. This may be documented in the subject's medical records or the study source documentation after discussion with the subject.*

4.3 Subject Recruitment

Subjects will be recruited by study site physicians or their delegate. Information about the study may be shared with patients by their caring physician or through patient advocacy groups. Patients may be contacted by IRB approved letter, email, or phone call.

4.4 Vulnerable Populations:

This study will enroll participants under the age of 18 years. Subjects 12 to 17 years of age will be asked to review the consent form and provide assent. A parent or legal guardian must provide informed consent for subjects under 18 years of age to participate.

5 Study Procedures

5.1 Informed Consent

This study will allow either written documentation of informed consent and assent or verbal consent and assent depending on the site preference and local requirements.

Written Informed Consent

Participants will be provided a consent form describing this study and providing sufficient information for subjects to make an informed decision about their participation. This consent form will be reviewed and approved by the IRB for the study.

Before initiating any study procedures, study personnel will review the study in detail and the subject will have the opportunity to have questions answered. At the end of the consent discussion, the subjects will be asked to sign the consent form and return it to the study team. The same study personnel, in the capacity of "persons obtaining consent" will sign the consent form of the subject after the consent conversation occurs. Consent conversations will be documented. A signed copy of the consent will be provided to the subject. Informed consent may occur prior to Visit 1.

For subjects under the age of 18, a parent or legal guardian will provide permission using the consent procedures described above. In addition, subjects 12 – 17 years of age will be asked to review the consent form and provide assent.

Verbal Informed Consent

As this is a minimal risk study with procedures for which written consent would not normally be required outside of the research setting, verbal consent is sufficient for enrollment into this study.

Subjects will be provided with a "Consent Information Sheet" describing this study and providing sufficient information for subjects to make an informed decision about their participation. This document will be reviewed and approved by the IRB for the study. Before initiating any study procedures, study personnel will review the study in detail and the subjects will have the opportunity to have questions answered.

When possible, recruitment and consent discussions will occur on separate days to allow subjects interested in participating time to review the participant information document prior to being asked to provide consent. Participants that would like to enroll remotely will have a scheduled phone or video call with the study personnel during which the consent discussion will take place. Consent discussions will be led by trained study personnel guided by the content of the Consent Information Sheet.

Consent discussions will be documented, signed, and dated by the study personnel obtaining informed consent in the 'Record of Verbal Consent' document. A participant will be considered enrolled after they have provided verbal consent and received a copy of the participant information document, and the rest of the study procedures may commence.

For subjects under the age of 18, a parent or legal guardian will provide permission using the verbal consent procedures described above. In addition, subjects 12 – 17 years of age will be asked to review the Consent Information Sheet and provide assent.

5.2 Medical Record Review

Variables to be abstracted from medical charts (paper or electronic) include elements that fall under the below categories, as available through routine clinical practice or obtained as part of this study:

- Contact information and socio-demographics
- Diagnoses
- Biometrics
- Physical exam
- Vital signs
- Pathology
- Laboratory results
- Clinical features
- Co-morbid conditions
- Medications (previous and current)
- Treatments, procedures, and surgeries
- End of study information (including information on early withdrawal)

5.3 Questionnaires

Subjects will be asked to complete several questionnaires, either standard surveys used routinely in clinical practice or as approved by the IRB. These questionnaires include:

- COVID-19 Community Response Survey: Comorbidities and Care Engagement, Coronavirus Impact and Pandemic Stress; Other COVID-19 Questions
- Participants 18-years of age and older:
 - Adult Sickle Cell Questionnaire-Me (ASCQ-Me) Measures
 - Emotional impact
 - Pain impact
 - Social functioning
 - Stiffness impact

- Sleep impact
- Brief COPE Scale⁸
- Brief Pain Inventory (BPI)
- Participants under 18 years of age:
 - PROMIS Pain Interference (8-17 years, or parent proxy)
 - Emotional Impact
 - Social Impact
 - Physical/Activity Impact
 - PROMIS Mobility (8-17 years, or parent proxy)
 - Impact on activities of physical mobility
- Additional surveys to assess health

5.4 Blood Draw

Up to 5ml of peripheral blood will be drawn at Visits 1, 5, and 6 to be tested for SARS-CoV2-specific antibody by enzyme-linked immunosorbent assay (ELISA). All biologic specimens will be shipped in a de-identified manner to [name] lab at the University of Pennsylvania for analysis of antibodies.¹⁰ All biospecimens will be destroyed at the completion of the study.

5.5 Schedule of Events

A table detailing the schedule of events is included in [Appendix A](#).

5.5.1 Visit 1

Visit 1 will occur up to 30 days prior to the subject's first or only COVID-19 vaccination. This visit may occur on the same day as vaccination, as long as study procedures are completed prior to vaccination. Some of the procedures may occur remotely as long as the participant provides consent prior to any research procedures commencing. The following procedures will be performed at Visit 1:

- Informed consent (if not previously completed)
- Medical record review and intake history
- Demographics
- Questionnaires:
 - COVID-19 Community Response Survey: Comorbidities and Care Engagement, Coronavirus Impact and Pandemic Stress; Other COVID-19 Questions

Participants 18-years of age and older:

- Adult Sickle Cell Questionnaire-Me (ASCQ-Me) Measures
 - Emotional impact
 - Pain impact
 - Social functioning
 - Stiffness impact
 - Sleep impact
- Brief COPE Scale
- Brief Pain Inventory (BPI)

Participants under 18 years of age:

- PROMIS Pain Interference (8-17 years, or parent proxy for participants <8)
 - Emotional Impact
 - Social Impact
 - Physical/Activity Impact
- PROMIS Mobility (8-17 years, or parent proxy for participants <8)

- Impact on activities of physical mobility
- Blood drawn for assessment of antibodies

Participants who enroll but do not receive the first vaccination within 30 days of consent should proceed in the study and the out of window vaccination should be documented as a protocol deviation. Future visits are benchmarked to the date of the first vaccination.

5.5.2 Visit 2

Visit 2 will occur 2-3 days following the first COVID-19 vaccination (or only vaccination if receiving a single dose vaccine. The subject will be contacted by phone, email, or text to complete a survey including information about the vaccine type received, side effects, and sickle cell disease related symptoms.

5.5.3 Visit 3

Visit 3 will occur 14 days (± 3 days) following the subject's first (only) COVID-19 vaccination. The subject will be contacted by phone, email, or text to complete a survey including information about side effects, and sickle cell disease related symptoms.

5.5.4 Visit 4

Visit 4 will occur 2-3 days following the second COVID-19 vaccination. If the subject received a single-dose vaccine, then Visit 4 will not occur. The subject will be contacted by phone, email, or text to complete a survey including information about the vaccine type received, side effects, and sickle cell disease related symptoms.

5.5.5 Visit 5

Visit 5 will occur 2 months (± 1 week) following the subject's first (or only) COVID-19 vaccination. If a subject received a two-dose vaccine and the receipt of the second dose is administered more than 5 weeks after administration of the 1st dose, then the Visit 5 should also be delayed to occur 3 to 4 weeks after the second vaccination. If the second vaccination does not occur by the initial Visit 5 window, Visit 5 should occur as scheduled and the missed/delayed 2nd dose documented.

The following procedures will be performed at Visit 5:

- Questionnaires:
 - Participants 18-years of age and older:
 - Adult Sickle Cell Questionnaire-Me (ASCQ-Me) Measures
 - Emotional impact
 - Pain impact
 - Social functioning
 - Stiffness impact
 - Sleep impact
 - Brief COPE Scale
 - Brief Pain Inventory (BPI)
 - Participants under 18 years of age:
 - PROMIS Pain Interference (8-17 years, or parent proxy for participants <8 years)
 - Emotional Impact
 - Social Impact

- Physical/Activity Impact
- PROMIS Mobility (8-17 years, or parent proxy for participants <8 years)
 - Impact on activities of physical mobility
- Kids Coping Scale⁹ (7-17 years)
- Blood drawn for assessment of antibodies
- Collection of information regarding COVID-19 diagnosis, sickle cell disease complications, and COVID-19 vaccine administration.

5.5.6 Visit 6

Visit 6 will occur 6 months (± 2 weeks) following the subject's first (or only) COVID-19 vaccination. The following procedures will be performed at Visit 6:

- Questionnaires
 - Participants 18-years of age and older:
 - Adult Sickle Cell Questionnaire-Me (ASCQ-Me) Measures
 - Emotional impact
 - Pain impact
 - Social functioning
 - Stiffness impact
 - Sleep impact
 - Brief COPE Scale
 - Brief Pain Inventory (BPI)
 - Participants under 18 years of age:
 - PROMIS Pain Interference (8-17 years or parent proxy for participants <8 years)
 - Emotional Impact
 - Social Impact
 - Physical/Activity Impact
 - PROMIS Mobility (8-17 years or parent proxy for participants <8 years)
 - Impact on activities of physical mobility
 - Kids Coping Scale⁹ (7-17 years)
- Blood drawn for assessment of antibodies
- Collection of information regarding COVID-19 diagnosis, sickle cell disease complications, and COVID 19 vaccine administration.

If a vaccine booster dose is planned during the Visit 6 window, the blood draw for assessment of antibody titers should be collected prior to administration of the booster dose whenever possible.

5.5.7 Unscheduled Visits

An unscheduled visit may occur if needed to obtain an additional blood sample as a result of a lab error, poor specimen collection, etc.

5.6 Subject Withdrawal and Early Termination

Subjects may withdraw from the study at any time without impact to their care. They may also be discontinued from the study at the discretion of the Investigator for lack of adherence to intervention or study procedures or visit schedules. The Investigator may also withdraw subjects to protect the subject for reasons related to safety or for administrative reasons. It will be

documented whether or not each subject completes the study. Subjects who withdraw early will be asked to have one final visit to collect final evaluations.

6 Statistical Plan

Statistical considerations were based on the available data for serum IgG ELISA titers for the Moderna vaccine administered at 50 ug mRNA-1293 at 56 days post initial vaccination (28 days post vaccination 2 for those patients receiving a product requiring two vaccinations). Data were obtained from Table 10 in the VRBPAC briefing document provided to the FDA dated 12/17/2020 (page 29).¹¹ Per that document, the average log10 titer was 5.750 with a standard deviation of 0.2765.

It is assumed that 200 individuals with sickle cell disease will receive an available vaccine. The vaccine product administered will be recorded and all products will be pooled for use for analyses; power calculations are based on a total of 200 participants. It is anticipated that 60% of participants will be of SS or Sbeta0thal genotype and 40% will be SC or Sbeta+thal or less common genotypes. The primary goal is to provide estimates of geometric mean titer at 2 months following initial vaccination with a 95% confidence interval. The geometric mean approach will be used to address asymmetry in the distribution of titers. Under these assumptions there will be more than 99% power to detect a drop to a geometric mean titer (GMT) to 5.50, assuming a two-sided 0.05 significance level and the reported standard deviation. This high level of power will be retained for the 120 SS or SBeta0thal patients and the 80 SC or SBeta+thal patients separately. Should the standard deviation for sickle cell patients be three times that reported for healthy controls in Table 10 of the briefing document, at least 90% power will still be retained for each of the genotypic subsets.

It is not yet known whether an immune response to vaccination might trigger vaso-occlusive crises or other consequences of sickle cell disease. Side effects reported in vaccinated participants will be described, with an estimate of rate with a confidence interval. Such events might enhance any vaccine hesitancy that may already exist in this population, leading some participants to decline the second vaccination if they receive an mRNA vaccine. Therefore, the rate at which patients receive only one dose of mRNA vaccine will be assessed. These participants will be retained in the study and titers will be measured at 2 and 6 months.

It is acknowledged that vaccines against other diseases established fold change in titer from pre to post vaccination, with established fold change criteria for protection. Such guidelines are not available for COVID-19, and therefore the titers will be examined at the specified time points. At this time there is data to suggest that vaccination leads to exceedingly high antibody titers, but there is no data to suggest clinical consequences for subjects whose titers increase substantially but are less than exceedingly high.

7 Safety and Adverse Events

An adverse event (AE) is any symptom, sign, illness or experience that develops or worsens in severity during the course of the study. Intercurrent illnesses or injuries should be regarded as adverse events. Abnormal results of diagnostic procedures are considered to be adverse events if the abnormality:

- results in study withdrawal
- is associated with a serious adverse event
- is associated with clinical signs or symptoms

- leads to additional treatment or to further diagnostic tests
- is considered by the investigator to be of clinical significance

Only adverse events with Grade 2 or higher per Common Terminology Criteria for Adverse Events (CTCAE) v5.0 determined by the investigator to be related to study procedures (phlebotomy) and occurring during the study period will be recorded. The clinical course of each related event will be followed until resolution, stabilization, or until it has been determined that study participation is not the cause. Adverse events related to a study procedure will be reported to the study sponsor and IRB, in accordance with IRB reporting requirements.

8 Study Administration, Data Handling and Record Keeping

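### Section 6 pools children and adults into one GMT and splits titers only by genotype, so a departure from 5.750 or a genotype difference could reflect age; add age-group GMTs (cheap improvement)

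*Combined protocol and SAP*

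**What the plan says.** **Who enters.** Section 4.4 states "This study will enroll participants under the age of 18 years". Section 4.1 sets no lower age limit. The Visit 1 questionnaires in Section 5.5.1 include "PROMIS Pain Interference (8-17 years, or parent proxy for participants <8", so children under 8 are allowed for. Any vaccine product is acceptable.

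**What is estimated.** The primary endpoint in Section 3.1 is one GMT at 2 months; the 6-month GMT is secondary. Section 6 makes the primary goal an estimate with a 95% confidence interval. On products it says "The vaccine product administered will be recorded and all products will be pooled for use for analyses".

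**The benchmark.** Section 6 opens with "Statistical considerations were based on the available data for serum IgG ELISA titers for the Moderna vaccine administered at 50 ug mRNA-1293" and reports that "the average log10 titer was 5.750 with a standard deviation of 0.2765". It later calls this group healthy controls and does not give its age range. It claims "more than 99% power to detect a drop to a geometric mean titer (GMT) to 5.50" for a two-sided test at 0.05 with that same SD, and adds that "power calculations are based on a total of 200 participants".

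**Subsets.** Genotype is the only titer subset named: 120 SS or Sbeta0thal participants and 80 others. Age serves to choose questionnaires and to settle consent and assent. Section 6 names no age stratum or age covariate, and the study has no concurrent control group.

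**The concern.** The pooled GMT is a weighted average of a child mean and an adult mean. The weights are whatever enrollment produces, and Section 6 neither fixes them nor commits to reporting them. The only outside figure offered for context comes from one product at one stated dose level, in a group whose ages are not given.

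If children and adults respond differently, the pooled GMT departs from 5.750 even when SCD has no effect. Lower titers in children would look like an SCD deficit; higher titers would hide one. The genotype estimates inherit the problem if one genotype group is younger. This bears on use of the results, because Section 1 says they should inform whether further doses are needed in this population. The planned output would give a reader no means of separating the explanations.

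**Working it through.** **1. The plan's own figure.** Inputs from Section 6: reference mean 5.750, target 5.50, SD 0.2765, two-sided 0.05. The drop is 5.750 - 5.50 = 0.25 log10, a factor of 10^0.25 = 1.78. For one mean against a fixed value, power = Phi(0.25/(SD/sqrt(n)) - 1.96).

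- n=200: 0.25/0.01955 = 12.8, so Phi(10.8)
- n=120: 0.25/0.02524 = 9.9, so Phi(7.9)
- n=80: 0.25/0.03091 = 8.1, so Phi(6.1)

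All exceed 99.9%, so the stated power of more than 99% reproduces at the reported SD. Nothing below changes it. The question is what a detected difference would mean.

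**2. Precision of the pooled mean.** The 95% half-width at N=200 is 1.96 x 0.2765/sqrt(200) = 0.038 log10. At Section 6's sensitivity value of three times the SD (0.8295) it is 0.115.

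**3. Shift from age mix.** Let f be the child share and d the child-adult difference in mean log10 titer. If adults sit at the reference mean and SCD has no effect, the pooled mean shifts by f x d. The documents give neither quantity. Assumed ranges are f = 10-50% and d = 0.1-0.3 in either direction (about 1.26- to 2-fold).

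- Smallest: 0.10 x 0.1 = 0.01, and 0.01/0.25 = 4% of the planned drop
- Largest: 0.50 x 0.3 = 0.15, and 0.15/0.25 = 60% of the planned drop

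The shift passes the 0.038 half-width when f exceeds 0.038/0.3 = 13% at d = 0.3, or 0.038/0.1 = 38% at d = 0.1.

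**4. Chance that age mix alone separates the pooled GMT from 5.750.** Setting: N=200, two-sided 0.05, no SCD effect, total SD = sqrt(SD^2 + f(1-f)d^2), with d = log10(fold difference).

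| Child share | Fold difference | Shift (log10) | SD 0.2765 | SD 0.8295 |
|---|---|---|---|---|
| 10% | 1.25 | 0.010 | 8% | 5% |
| 10% | 2 | 0.030 | 31% | 8% |
| 25% | 1.5 | 0.044 | 58% | 12% |
| 25% | 2 | 0.075 | 94% | 25% |
| 50% | 1.5 | 0.088 | 99% | 32% |

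**5. Genotype comparison.** The spurious difference is (f1 - f2) x d. At the far ends of the assumed range, 50% against 10% children, it is 0.4 x 0.1 = 0.04 to 0.4 x 0.3 = 0.12 log10. With equal child shares it is zero.

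**6. Precision after an age split.** Half-width = t x SD/sqrt(n), with t = 2.01 at n=50 and 2.093 at n=20 (25% and 10% of 200).

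| n in age group | SD 0.2765 | SD 0.8295 |
|---|---|---|
| 50 | 0.079 (factor 1.20) | 0.236 (factor 1.72) |
| 20 | 0.129 (factor 1.35) | 0.388 (factor 2.4) |

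**The case against.** The best defense is that this is an estimation study. Its objective is to measure response in a cohort, and its endpoint is a GMT with an interval. The value 5.750 enters only as a planning figure, and nothing commits the sponsor to test or report against it. That stands. A reader might infer that an age difference would be taken for an SCD effect; the documents support only that it could be. Still, the power paragraph is the plan's one inferential statement on titers and is framed as a drop from 5.750, so the comparison is easy to make.

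A reader might also infer that children received different dose levels, or that the amount given goes unrecorded. Neither is supported. The documents give no age-specific dosing. Visits 5 and 6 collect vaccine-administration information and Section 5.2 abstracts medications and treatments; the forms are not included, so whether they capture the amount is unknown.

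The 60% figure is a corner case needing half the cohort to be children and a two-fold difference. The under-8 proxy forms show that such children are permitted, not how many are expected. That is right, and the range starts at 4%.

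Finally, an age split is not precise in every case. With 20 children, or at three times the SD, the intervals are wide: 0.236 at n=50 is 94% of the 0.25 drop. That also stands and limits the age-group results to description. It does not justify leaving the age mix unreported, because Visit 1 already collects demographics.

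**Conclusion.** The point holds as a cheap improvement. With pooling across ages, one external reference and a genotype-only split, the planned output cannot distinguish an age difference from an SCD difference, or from a genotype difference where age mix differs. The direction is unknown. The size is also unknown: the 0.01-0.15 log10 range rests wholly on the assumed child share and child-adult difference, and on adults sitting at the reference mean. At the reported SD, the middle and upper part of that range exceeds the pooled interval's half-width. At three times the SD, only shifts above 0.115 do.

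The documents do not support reading this as an error in the power figure or an invalid primary endpoint. Any dose-level explanation remains conditional on data not shown.

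**What to change.** In Section 6:

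1. Keep the pooled GMT as primary. Add GMTs with 95% confidence intervals at 2 and 6 months for participants under 18 and for those 18 or older, labeled descriptive.
2. Report the age mix, overall and by genotype group.
3. Present genotype results adjusted for age group.
4. State that 5.750 is a planning value. Make any comparison with it descriptive, and limit it to participants comparable to the reference group in product and, once confirmed from the cited briefing document, age range.
5. If existing vaccine-administration or chart data show more than one dose level within a product, describe titers by dose level too.

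The cost is a few sentences in Section 6 and some extra tables, with no new visits or samples. The downside is the wider age-group intervals shown in step 6 of the working. A split at 18 also leaves children under 8 grouped with adolescents, so the age-mix table should show how many there are.
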